Given the mixture distribution of the EQ-5D-5L (the component of zero and the component other than 0), we will specify separate priors per longitudinally assessed outcome. Consequently, we will specify a prior for the mean difference with an EQ-5D-5L other than 0 and a prior for the proportion of patients who have an EQ-5D-5L score of 0 (i.e., deceased patients). This longitudinal analysis will be performed with adjustment for center as a random effect. The results of the analyses for the components will be presented separately and as weighted averages.

Analysis of longitudinally assessed secondary outcomes

Secondary outcomes for which no prior evidence was available will be estimated under a weakly informative prior, in a model similar to the longitudinally assessed primary outcome, with adjustment for the random effect of center.

Analysis of outcomes at one given time point

Secondary binary outcomes, such as 60-day mortality, will be expressed in ORs and absolute risk differences (ARD). These binary outcomes will be analyzed in a binary mixed regression model (Bernoulli distribution) with an adjustment for the random center effect. Priors for these binary outcomes are presented on the log OR scale in Table 1. Other secondary continuous outcomes, such as the duration of mechanical ventilation, will be reported in mean differences (MD) for the specific units of that endpoint. Finally, the abovementioned mixture distribution (the component of zero, and the component other than 0) will be used for the EQ-5D-5L assessment at the cross-sectional time points, and separate priors will be formulated, similar to the primary outcome assessment.

Handling of missing data

As the missingness of data is assumed to be missing at random (MAR), the linear mixed effects model will be appropriate to handle missing data.

Model settings and diagnostics

The models for our analysis will be implemented in *JAGS* using Markov Chain Monte Carlo (MCMC) algorithms, through the *R2jags* package (20, 21). Assessment of model convergence will be performed for key model parameters via potential scale reduction factors (Rhat) effective sample size (ESS), and other diagnostics such as density and trace plots. Model fit will be assessed in relative terms through the deviance information criterion (DIC and other criteria alike), and in absolute terms using posterior prediction checks (PPCs).

(Serious) Adverse events

Due to the nature of the patient population (i.e., critically ill patients), all participants entered the study in a state of life-threatening illness and were likely to experience many events that could be classified as an (S)AE. Therefore, only SAEs which result in death or life-threatening situations due to complications with study nutrition were reported.

In addition, several events of special interest will be compared between groups to compare the safety and harm of the two study feeds. These include:

- Incidence of ventilator-acquired pneumonia
- Incidence of acute kidney injury
- Refeeding hypophosphatemia
- Incidence of hepatic dysfunction
- Incidence of gastrointestinal intolerance/symptoms

These events are further specified in **Appendix 3**.

Statistical software

The statistical analysis and reporting will be done using R (version 4.3.1 or higher) and the code will be published on an online repository (included in the supplemental appendix).

References

2. van Gassel RJJ, Bels JLM, Tartaglia K, van Bussel BCT, van Kuijk SMJ, Deane AM, et al. The impact of high versus standard enteral protein provision on functional recovery following intensive care admission (PRECISE trial): study protocol for a randomized controlled, quadruple blinded, multicenter, parallel group trial in mechanically ventilated patients. Trials. 2023;24(1):416.

6. EQ-5D-5L User Guide. https://euroqol.org/publications/user-guides: EuroQol Research Foundation; 2019.

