The PRECISe trial is a bi-national, quadruple-blinded, multicenter randomized controlled trial (RCT) assessing the superiority of high versus standard enteral protein provision in mechanically ventilated ICU patients. (2)

Randomization

A computer algorithm was used to generate the concealed, random allocation sequence. Patients were randomized in a 1:1 ratio, stratified per center, using block randomization with random permuted block sizes varying between 4 and 6.

Sample size

The sample size calculation was based on a published cross-sectional measurement of the EQ-5D-5L health utility score at 180 days following ICU admission, as longitudinal data were unavailable (3). A minimum difference of 0.06 points on the EQ-5D-5L health utility score was selected to represent the minimum clinically important between-group difference to be detected. (4)

Based on these data, the sample size for the PRECISe trial was calculated as follows: assuming a standard deviation (SD) of 0.3 at 180 days (3), considering a two-sided type I error rate α of 5% and a type II error rate β of 20% (yielding a statistical power of 80%), 392 participants per intervention group will be required to detect the minimum clinically important difference of 0.06 in the EQ-5D-5L health utility score. In line with other critical care trials, the sample size has been adjusted upwards for an estimated 5% loss to follow-up for the primary endpoint. (5) After this adjustment, the final sample size for the PRECISe trial was set at 824 participants.

During the preplanned interim safety analysis after inclusion of 50% of patients, it became apparent that mortality was higher than anticipated, resulting in a standard deviation of the EQ-5D-5L HUS that was larger than expected (0.38 vs 0.30). Since this potentially could reduce the power of the study, the DSMB advised to increase the sample size. By running a Monte Carlo simulation of the primary outcome analysis using raw longitudinal data of the actual study population at that time (n = 709), without unblinding, it was calculated that with the observed standard deviation, a sample size of 935 patients would be required to retain 80% power to detect the minimally important difference of 0.06, while correcting for the actual loss-to-follow-up rate of 9.4%.

Framework

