- Domain data EQ-5D-5L: scores of subdomains of EQ-5D-5L at 30, 90, and 180 days after admission, with higher scores indicating increased impairment.
- Return to work: number of patients who return to work, and number of days between ICU admission and return to work.

Outcomes regarding protocol adherence are discussed separately under "Adherence and protocol deviations".

Lastly, a health economic evaluation will be performed. Details of this analysis are discussed separately under "Additional analyses".

Unblinding

To mitigate the consequences of an accidental unblinding during the trial, 4 randomization labels (A, B, C, D), were used. Each study group was coded by two different labels. The trial will be unblinded in a stepwise manner. After database lock, it will be revealed which two labels, , each belong together to form one of the groups (i.e., either the high protein or the standard protein group), but it will not yet be revealed which group they actually belong to. Therefore, subsequent analysis of the endpoints will be performed blinded. Only after the analyses are finalized, it will be revealed which group of labels is the high protein group and which group is the standard protein group. This way, the analyses will be done in a blinded fashion, preventing bias.

Analysis methods

Primary outcome

The primary outcome will be analyzed using a linear mixed effects model with a 3-level structure, i.e., repeated measurements are clustered within participants and participants are clustered within centers. The fixed factors are treatment group, time, treatment group*time, and baseline EQ-5D-5L.

With respect to the random-effects, two models will be considered: a random intercepts model and a random intercepts and slope model. The model with the lowest Akaike Information Criterion (AIC) will be selected. Correlations between follow-up measurements will be modelled either using an autoregressive model of the first order (AR1) or left unstructured. Again, the AIC will be used to select the model with the best fit to the data.

Homoscedasticity of the residuals will be assessed using Levene's test and inspected using residual plots. Normality of the residuals will be assessed using QQ-plots. In case of violation of homoscedasticity, the model will be extended with a variance function; in case of violation of normality, the outcome will be transformed. If the assumption is still violated after transformation, we will apply a robust mixed-effects fit.

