As sensitivity analysis, the model will be further adjusted for sex, APACHE II score, APACHE IV admission diagnosis, and NRS-2002.

Secondary and tertiary outcomes

Survival outcome

For the secondary endpoint overall survival, survival curves for both treatment arms will be constructed using the Kaplan-Meier method. Then, a Cox proportional hazards frailty model, with a 2-level structure, i.e., participants clustered within centers, will be used to investigate a treatment effect. The crude, unadjusted Hazard ratios will be reported with a 95% confidence interval. The proportional hazard assumption will be assessed as the association between the scaled Schoenfeld residuals and follow-up time. Additionally, sensitivity analyses will be performed by adjusting for potential confounders (sex, APACHE II score, APACHE IV admission diagnosis, and NRS-2002) is similar as described for the primary endpoint analysis.

Longitudinally assessed outcomes

The treatment effects for longitudinally assessed secondary and tertiary endpoints (SF-36, HADS, IES-R, EQ-5D-5L (EQ-VAS and pain question), 6-minute walking distance, MRC-SUM, and handgrip strength, frailty assessed by Rockwood Clinical Frailty Scale and mean and maximum SOFA scores) are assessed using linear mixed-effects models. The statistical approach will be similar as described for the analysis of the primary endpoint, particularly concerning the calculation of between-group differences, the 3-level model structure (with fixed treatment effect and random effects for center and participants), reporting of effect size, adjustment for potential confounders, and model selection strategy.

Time-to-event outcome

For time-to-discharge-alive from hospital, data of non-survivors will be censored at a time point beyond that of the last surviving patient to account for death as a competing risk. Between-group differences will then be estimated similar to overall survival.

Categorical outcomes

The differences in all categorical tertiary outcomes (see **Appendices 3-5**) will be analyzed using Pearson's chi-square test or Fisher's exact test, as appropriate. The treatment effects on all other tertiary outcomes will be analyzed using the Student's t-test or Mann-Whitney U test, depending on the distribution of data.

Subgroup analyses

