The assumed missing data mechanism for all endpoints is missing at random (MAR), given the amount of baseline covariates and other outcome variables collected. Longitudinal endpoints will be analyzed using mixed-effects models. This approach is robust with regard to MAR provided that variables contributing to the mechanism are used as covariates in the model.

In practice, baseline or outcome covariates will be introduced to the model if more than 5% of outcome data are missing. The baseline covariates in Table 1 and other outcome variables will be tested and added to the model if they are associated with the outcome or with a missingness indicator in univariate analysis with a P-value of < 0.05.

Missing data in other outcome data (not longitudinally assessed) and baseline covariates will be imputed using multiple imputation with fully conditional specification, in case the rate of missing data is more than 5%.

As a sensitivity analysis, we will perform the analysis of the primary outcome without modelling the MAR mechanism to test the robustness of our assumption.

Additional analyses

Health economic evaluation

The main question for the economic evaluation is to assess whether high enteral protein provision is cost-effective compared to standard enteral protein provision. The economic evaluation will be performed from a health care perspective over 180 days from ICU admission.

To quantify health care costs, data regarding ICU and hospital resource use will be collected, using the Dutch (Zorginstituut Nederland) and Belgian (RIZIV) guidelines for cost calculation. (14, 15) The following variables will be collected to quantify the most important medical costs within and outside

the hospital incurred by ICU patients: duration of mechanical ventilation, ICU and hospital length of stay, ICU and hospital readmissions, days on renal replacement therapy, days on intravenous antibiotics, complications, and admission to and duration of stay in a rehabilitation center.

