Appendix 5. Trial termination characteristics

Variable	Definition	Type of data
Rehabilitation center	Admission to rehabilitation center during follow-up period	Binary,
admission	and duration of stay in days	continuous
Return to work	Return to work (if applicable) and date of work resumption	Binary, date
Death	Survival status and date of death (if applicable)	Binary, date
Early trial termination	Reason for early trial termination, e.g., due to death or proxy or patient consent withdrawal, and date of early termination	Nominal, date
Unblinding	Occurrence of unblinding during trial participation	Binary

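### Days to return to work would in effect be compared among returners only, a group formed after randomisation, so this comparison can mislead in either direction

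*SAP*

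**What the plan says.** Among the tertiary functional outcomes in Section 5 (Outcome definitions) the SAP lists "Return to work: number of patients who return to work, and number of days between ICU admission and return to work". This has two parts, a count and a duration.

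The Analysis methods part of Section 5 assigns a method by type of outcome:

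- Return to work is not among the longitudinal outcomes.
- The paragraph on time-to-event outcomes names only time to live discharge from hospital. For that outcome, "data of non-survivors will be censored at a time point beyond that of the last surviving patient", so that death is handled as a competing risk. Estimation then follows overall survival, that is, a Cox frailty model with centre.
- Categorical tertiary outcomes "will be analyzed using Pearson's chi-square test or Fisher's exact test, as appropriate". This covers the number returning.
- For the remainder: "The treatment effects on all other tertiary outcomes will be analyzed using the Student's t-test or Mann-Whitney U test". The days to return fall here.

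Appendix 5 describes what is recorded: "Return to work (if applicable) and date of work resumption". The rule that gives deaths a score of 0 (Section 4, Withdrawal/follow-up) covers the primary outcome only. Under Missing data, "Missing data in other outcome data (not longitudinally assessed) and baseline covariates will be imputed using multiple imputation with fully conditional specification" when more than 5% is missing; nothing is said there about patients who died or did not go back to work.

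**The concern.** A number of days to return can be computed only for a patient who returned. A t-test or rank test on that variable therefore compares those who returned in one arm with those who returned in the other. Membership of that group is decided after randomisation, by an event that the treatment may influence, so the two sets of returners need not be comparable.

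Deaths are not a marginal part of what is lost. The Sample size section reports that at the interim safety analysis "it became apparent that mortality was higher than anticipated", although it gives no rate. Patients alive but not yet back at work when follow-up ends are lost from the comparison too.

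At stake is how a difference in days would be read. An arm in which more patients get back to work may show a longer mean time, and an arm in which fewer do may show a shorter one. The SAP recognises this structure, a favourable event that death precludes, for discharge alive and deals with it there, but not here.

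**Working it through.** The SAP gives no employment rate, return rate or return time, so there is no figure of its own to reproduce. All rates and days below are assumptions, chosen to show direction and size.

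**1. Which patients enter the test.** The outcome list defines the days, the default rule assigns the test, and Appendix 5 supplies a date only where work was resumed. Together these leave returners only. The one other route is the imputation rule. If 40% of previously working patients return, 60% have no day count, far above the 5% trigger. Imputation would then create return dates for patients who died or never went back, which does not repair the comparison.

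**2. Direction, by arithmetic.** Suppose that in arm A 40% return at a mean of 100 days. In arm B the same 40% return at the same times and a further *e*% return at day *d*. The mean in B is (40 × 100 + *e* × *d*) / (40 + *e*).

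| *e* | *d* | Mean in B (days) | B minus A (days) |
|---|---|---|---|
| 10 | 160 | (4000 + 1600)/50 = 112 | +12 |
| 5 | 160 | (4000 + 800)/45 = 106.7 | +6.7 |
| 20 | 160 | (4000 + 3200)/60 = 120 | +20 |
| 10 | 100 | (4000 + 1000)/50 = 100 | 0 |
| 10 | 60 | (4000 + 600)/50 = 92 | −8 |

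Nobody in B is worse off in any row. B looks slower only when the added returns come later than the mean of 100 days in A. Reversing the arms in the first row gives the mirror case: a treatment that prevents late returns looks 12 days faster while fewer patients go back. If treatment only brings the same 40% back 10 days sooner, the means are 90 and 100 and the sign is right.

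**3. How often a test would be significant.** A simulation used 467 patients per arm (935/2, rounded down), two-sided alpha 0.05 and 1,000 runs per scenario. It assumed that 30–50% worked before ICU admission and that 30% of these return under control, at about 110 days (SD 35). Treatment leaves those returns unchanged and adds returns at about 150 days in 5–20% of those who would otherwise not return.

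- With 40% working and 15% added, return rises from 30% to 30 + 0.15 × 70 = 40.5% (about 40% in the runs). Among returners the treated mean is 10.5 days longer. The difference is significant in the apparent-harm direction in 45% of trials by Mann-Whitney and 42% by t-test, and in the benefit direction in none by Mann-Whitney.
- A rank test in all previously working patients, with deaths and non-returners ranked after every return time, shows significant benefit in 36% and harm in 0.1%.
- Over the whole range, the returners-only Mann-Whitney test shows apparent harm in 8% (30% working, 5% added) to 72% (50% working, 20% added). The all-patient test shows benefit in 7% to 65% and harm in at most about 1%.
- With no treatment effect, both tests reject in about 5% of trials or fewer.

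Every non-null scenario adds late returns, so these rates show what that pattern does and not how likely the pattern is.

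**The case against.** The strongest reply is that the outcome has two parts and the first is sound. The number returning is tested separately, so in the illustration a report would show 50% against 40% returning next to the 12-day difference. Overall survival is a secondary outcome as well. This stands: a reader might infer that the SAP ignores deaths and non-returners altogether, and it does not. They are lost from the days comparison only.

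Secondly, the SAP nowhere says that days are compared among returners only, and it states that all analyses are by intention to treat. A reader might take the restriction to be a stated plan. It is instead what the definition of the variable and the default test produce together. The intention-to-treat statement does not remove it, because no value is assigned to patients without a return date.

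Thirdly, a reader might infer that the bias reverses the meaning of a benefit. The documents do not support that. Reversal needs the added returns to be mainly late, and nothing in the SAP says that they would be.

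Finally, the SAP describes its analyses as a minimum, so a time-to-event analysis could still be added. That is true, but the prespecified test would remain.

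**Conclusion.** The point holds, with low weight. As written, the SAP sends days to return to work to a test that in effect compares groups selected after randomisation, and the result can be biased in either direction. In the assumed illustration the arm with more returners looks 12 days slower; other inputs give a zero difference or one in the right direction. The conclusion that the comparison is conditioned on a post-randomisation event rests on the SAP's text alone. The sizes rest wholly on assumed employment, return and timing figures. One component of one tertiary outcome is affected, and no primary or secondary conclusion depends on it. The SAP already contains a better method, for discharge alive.

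**What to change.** Move return to work into the time-to-event paragraph. Analyse time from ICU admission to return in all randomised patients to whom it applies, that is, those working before ICU admission. Censor non-returners at the end of follow-up and handle death as a competing event in the way already set out for discharge alive, whose model also carries centre. Keep the test of the number returning.

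The dates of work resumption and of death are already collected (Appendix 5), but the denominator is less certain. Appendices 1 and 2 list no variable for employment before admission; the only trace is the qualifier on applicability in Appendix 5. The sponsor should confirm that this field identifies previously working patients in both arms, including those who died early. If it does not, report days among returners descriptively, without a between-group test, and base the comparison on the number returning.

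The cost is a few sentences in the SAP, one check of the database field, and slightly more analysis work on a tertiary outcome.

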A superiority hypothesis testing framework will be used for primary and secondary outcomes. The null hypothesis is that the mean EQ-5D-5L health utility score of the intervention group is equal to the mean EQ-5D-5L health utility score of the control groups.

Timing of final analysis

The final analysis for all endpoints is planned when 180 days of follow-up is completed for the last surviving patient included.

Timing of outcome assessments

Outcome assessments occurred 30, 90, and 180 days after ICU admission. A window ranging from 4 days before to 4 days after the calculated follow-up date was defined, within which outcomes were collected.

Section 3. Monitoring of the trial

eCRF and database

All study data, including questionnaires, were recorded and stored in an electronic case report form (eCRF) created with the CASTOR[©] software (Castor, Amsterdam, The Netherlands). To protect the participants' privacy, all collected data is encoded, consisting of a code specific to the recruitment site, the study's abbreviation (PRECISe) and an incremental 3-digit number per center (starting from 001 in order of inclusion). Data will be exported for analysis as a comma-separated file (.csv), Excel file (.xlsx), and SPSS file (.data). Data management was performed by the Clinical Trial Unit of Ziekenhuis Oost-Limburg A.V. A clinical research organization (Clinical Trial Center Maastricht) was responsible for source data verification.

Data Safety Monitoring Board

A data and safety monitoring committee has overseen the trial at regular, predefined intervals to protect and serve the safety of trial participants and protect the validity and credibility of the trial results.

Statistical interim analyses and stopping guidance

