The progress of all patients through the trial will be displayed as part of the CONSORT flow diagram. The number of patients who did not receive the allocated intervention will be reported, including corresponding reasons. Number of patients for whom no endpoints could be collected due to early withdrawal, and reasons for withdrawal, will be reported per trial phase. Patients who died will receive a score of 0 for the primary outcome and will be included in the final analyses, as described in the EQ-5D-5L user guide provided by the EuroQol Research Foundation. (6)

Baseline patient characteristics

The baseline characteristics in Table 1 will be summarized per treatment arm.

Age	Sex	BMI
Type of admission	Admission diagnosis system	ICU admission due to COVID-19 infection
Sepsis	Acute kidney injury	Glasgow Coma Scale
History of diabetes mellitus	APACHE II score	APACHE IV score
SAPS II score	SOFA score	EQ-5D-5L health utility score
Charlson Comorbidity Index	Rockwood Frailty Score	NRS-2002 score

Table 1. Baseline characteristics of the PRECISe trial.

BMI, Body Mass Index; ICU, Intensive Care Unit; COVID-19, Coronavirus Disease 2019; APACHE, Acute physiology and chronic health evaluation; SAPS, Simplified Acute Physiology Score; SOFA, Sequential Organ Failure Assessment; EQ-5D-5L, Euro-QoL-5D-5-level; NRS-2002, Nutritional Risk Screening 2002.

Section 5. Analysis

The purpose of this Statistical Analysis Plan (SAP) is to provide a comprehensive and detailed description of the methods of data analyses proposed for the PRECISe trial. This SAP is based on the study protocol version 5.0 (the Netherlands) and 4.0 (Belgium). The SAP is written in concordance with the guideline for statistical analysis plans, formulated by Gamble et al. (7)

The SAP will define the analyses that will minimally be executed. Statistical analysis will be performed under the responsibility of the authors of the SAP, under the supervision of the trial statistician, while following the statistical principles as formulated in the International Council for Harmonisation (ICH) guideline. (8) This SAP is reviewed and approved by the Trial Steering Committee.

Outcome definitions

Primary outcome

The primary outcome is health-related quality of life, assessed by the overall difference in EQ-5D-5L health utility score between the intervention and control groups over three time points (30, 90, and 180 days after ICU admission), adjusted for baseline EQ-5D-5L.

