The health utility score is derived from the responses to the 5-item EQ-5D-5L questionnaire, which is converted into a 5-digit number and then weighted using country-specific value sets, resulting in the EQ-5D-5L health utility score. The health utility score ranges from -0.532 to 1.0, with a score of 0 indicating death, a score below 0 indicating a state worse than death, a higher score indicating better health, and a score of 1 indicating perfect health.

Secondary outcomes

Clinical outcomes

Overall survival up to 180 days after ICU admission, with the use of Kaplan–Meier plots and a Cox proportional-hazards model, after ensuring, with the Schoenfeld residuals method, that the proportional-hazards assumption was met.

Functional outcomes

The following outcomes are collected at 30, 90, and 180 days after ICU admission.

- Health-related quality of life assessed by the Short Form 36 (SF-36): overall score, physical component score (PCS), and mental component score (MCS). Overall score ranges from 0 to 100, with higher scores indicating better Health-related Quality of Life.
- Anxiety and depression, assessed by the Hospital Anxiety and Depression Scale (HADS): oddnumbered questions measure symptoms of anxiety, and even-numbered questions measure symptoms of depression. Overall score ranges from 0 to 42, with higher scores indicating worse symptoms of anxiety and depression.
- Pain intensity assessed by the EQ-5D-5L pain question: ranges from 1 to 5, with higher scores indicating a more severe perception of pain or discomfort.
- Self-reported health assessed by the EQ-5D-5L visual analogue scale (EQ-VAS): ranges from 0 to 100, with higher scores indicating better self-reported health.
- Post-traumatic stress assessed by the Impact of Event Scale-Revised (IES-R): ranges from 0 to
 88, with higher scores indicating worse symptoms of post-traumatic stress.
- Physical function assessed by 6-minute walk distance: total distance (meters) covered over a time of 6 minutes, standardized for sex and age.
- Muscle and nerve function assessed by Medical Research Council (MRC)-sum score: ranges from 0 to 60, with higher scores indicating better muscle and nerve function.
- Muscle and nerve function assessed by handgrip strength: measured using a hand dynamometer and expressed in kilograms, standardized for sex and age.

Tertiary outcomes

Clinical outcomes

- Hospital mortality: number of patients who died during index hospital admission.

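### A likely failure of the QQ-plot check would move the primary analysis to an unnamed transformation, then to an unnamed robust fit, away from the utility scale on which the null, the 0.06 difference and N=935 are set

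*SAP*

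**What the plan says.** The Outcome definitions section fixes the primary endpoint on the utility scale: "assessed by the overall difference in EQ-5D-5L health utility score between the intervention and control groups over three time points". The Framework section puts the hypothesis on the same scale: "The null hypothesis is that the mean EQ-5D-5L health utility score of the intervention group is equal to" that of the control group. The Sample size section sets the target difference of 0.06 and the revised N of 935 in utility units.

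Under Withdrawal/follow-up: "Patients who died will receive a score of 0 for the primary outcome". That value lies inside the scale: "The health utility score ranges from -0.532 to 1.0".

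The primary model is a three-level linear mixed model on the utility score. For its residuals, Analysis methods (Primary outcome) says: "Normality of the residuals will be assessed using QQ-plots". No criterion is given. Two steps follow: "in case of violation of normality, the outcome will be transformed", and then "If the assumption is still violated after transformation, we will apply a robust mixed-effects fit". The text names no transformation, shift, back-transformation, robust estimator or tuning constant, and does not say whether the robust fit uses the raw or the transformed outcome. Nothing keeps the untransformed contrast as the primary result if normality fails.

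The Bayesian section starts its treatment of the same outcome from a different description: "Given the mixture distribution of the EQ-5D-5L (the component of zero and the component other than 0").

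**The concern.** The rule is conditional, but its condition is foreseeable. An outcome that the SAP itself describes as a spike at 0 plus a spread of other values will very likely not give straight QQ-plots. An order-preserving transformation moves the spike but cannot spread it out, so the second step is likely to be reached as well.

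What is at stake is the quantity estimated. If a transformed fit is accepted, or the robust fit is run on transformed data, the trial still tests a difference between arms, but not the difference in utility that defines the outcome. The estimate and interval can then not be set against 0.06, and the power behind N=935 no longer applies. The transformation also decides how much a death counts relative to a change in survivors' quality of life. Because scores go below 0, a log or square root needs an arbitrary shift or reflection that the SAP does not fix.

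The rule reaches further. The subgroup analyses take over the primary model specification, and the longitudinal secondary and tertiary outcomes follow a similar approach.

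**Working it through.** **The plan's own figures are in utility units.** From the Sample size section (SD 0.30, difference 0.06, two-sided 5%, 80% power): n = 2 × (1.960 + 0.842)² × 0.30² / 0.06² = 392.4 per arm (stated 392). Then 392 × 1.05 = 411.6, rounded to 412, and 2 × 412 = 824 as stated. The revised N=935 came from a simulation on trial data and cannot be recomputed, but it targets the same 0.06 with SD 0.38 and 9.4% loss.

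**Assumptions.** The SAP gives no death rate, so four day-180 rates are shown: 15, 25, 35 and 45%. Survivors follow a beta distribution on -0.532 to 1.0 (means 0.58 to 0.76, latent between-visit correlation 0.6). SD by visit is 0.34 to 0.41, with 935 patients, 10 centres and 9.4% of visits missing. The model has centre and patient random intercepts, treatment, time, their interaction and baseline; the contrast is averaged over visits.

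**Step 1: will the check fail, and does a transformation help?** Correlation of the QQ-plot of visit-level residuals:

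| Deaths by day 180 | Untransformed | Straightest Yeo-Johnson power |
|---|---|---|
| 15% | 0.993 | 0.999 |
| 25% | 0.984 | 0.994 |
| 35% | 0.959 | 0.985 |
| 45% | 0.932 | 0.969 |

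Truly normal data give 0.9996 (1st percentile 0.9991). A transformation may pass near 15% deaths and falls short from 25%. A separate simulation at the same death rates gave 0.997, 0.985, 0.978 and 0.960 untransformed, again not repaired from 25% upward.

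**Step 2: a limit that needs no survivor model.** For the outcome at one visit, with share p tied at 0, no order-preserving transformation can exceed a QQ correlation of √(1 − p × V), where V is the variance of a standard normal within the tied block. At p = 0.25 with nobody below 0, V = 0.2416 and √(1 − 0.25 × 0.2416) = 0.969. With 5% below 0, V = 0.0938 and the limit is 0.988. At 35% deaths the limits are 0.948 to 0.975, at 45% 0.921 to 0.956. This concerns the outcome, not the model residuals.

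**Step 3: what a transformed result would show.** With a true difference of 0.06 in mean utility:

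| | Likelihood-fitted power | Straightest-QQ power |
|---|---|---|
| Estimate on the new scale | 0.05 to 0.10 | 0.15 to 0.86 |
| Test statistic relative to raw, effect through survivors | 0.92 to 1.07 | 1.09 to 1.81 |
| Test statistic relative to raw, effect through deaths | 0.96 to 1.01 | 0.82 to 0.89 |

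If the raw analysis has 80% power, a ratio r gives Φ(r × 2.802 − 1.960): 73% at 0.92, 85% at 1.07, 63% at 0.82 and over 99% at 1.81.

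A simpler calculation gives the same message. It uses one visit without baseline adjustment, 935 × 0.906 / 2 = 423.6 patients per arm, control deaths 40%, survivor mean 0.65 and SD 0.27 (overall SD 0.38). Power is Φ(d / (s√(2/423.6)) − 1.96), with d and s the difference and SD on the scale analysed:

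| Scale | 0.06 through fewer deaths | 0.06 through better survivors |
|---|---|---|
| Raw | 64% | 58% |
| log(y + 0.533) | 68% | 37% |
| (y + 0.532)² | 59% | 77% |
| −√(1 − y) | 57% | 90% |
| −log(1.01 − y) | 45% | 99% |

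For the raw scale with fewer deaths: 0.0603 / (0.378 × 0.0687) − 1.96 = 0.36, and Φ(0.36) = 0.64. The levels are below 80% because only one visit is used; the comparison between rows is what matters.

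**Step 4: robust fit on the raw outcome.** Huber weights on visit residuals and patient intercepts gave estimates −1% to +7% from the mean difference at constants 1.68 to 2.28, +6% to +18% at 1.345, and +1% to +36% at 1.08.

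**Step 5: is the untransformed contrast safe?** Nominal 95% intervals covered the truth in 94.6 to 96.4% of simulated trials (model-based) and 94.8 to 96.4% (patient-level sandwich, centre effect kept). Sandwich standard errors were 0.3 to 0.7% larger. A bootstrap of patients within centre and arm covered 93.2 to 93.6% over 250 trials, within simulation error of 95% (standard error √(0.95 × 0.05 / 250) = 1.4 percentage points).

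**The case against.** The strongest reply is that the serious harm lies on the less likely branch. If transformation fails, the analysis ends in a robust fit, and on the raw outcome that fit stays in utility units and usually near the mean difference. This stands. It still leaves the scale of that fit and its tuning constant open, and Step 4 shows that the constant matters.

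A test on a transformed scale also remains valid when the two arms have identical distributions, and the Objectives section states its null without the word mean. That stands too, but the Framework null is on the mean, and an effect estimate needs a unit whichever null is used. Fitted means could be converted back to utility, but the SAP does not say so.

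With a likelihood-fitted power the test statistic hardly moves, and the largest figures come from the straightest-QQ power, which at 45% deaths lies at the edge of the grid searched. This is fair: those figures show how far an unnamed choice can reach, not what to expect. Likewise the limit in Step 2 applies to one visit, and the simulated residuals exceed it, so Step 1 carries the argument. Random slopes, AR1 and unstructured correlations were not simulated.

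The preplanned Bayesian analysis already treats the outcome in two parts, and the SAP lists only the minimum of analyses, so an untransformed fit could be reported alongside. Neither makes the untransformed contrast the primary result. Arm identity is masked during analysis; that limits directional choice but does not settle what is estimated.

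**Conclusion.** The concern holds and should be fixed. The SAP states a mandatory rule that is very likely to be triggered, leaves both of its steps unnamed, and lets the primary result leave the scale on which the outcome, the null, the 0.06 difference and N=935 are defined.

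The size depends on the branch taken. A robust fit on raw data at common constants shifts the estimate by −1% to +18%. An accepted transformation puts it in other units and changes the test statistic by anything from almost nothing to a factor of 0.82 to 1.81 in the main runs; the separate simulation, over its own choice of transformations, gave about 0.74 to 2.7 for a survivor effect and 0.77 to 1.03 for a mortality effect. All these figures rest on assumed death rates and survivor distributions. What does not rest on them is that the text fixes neither the method nor the scale.

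**What to change.** In Analysis methods (Primary outcome), state that the treatment contrast from the untransformed three-level mixed model, a difference in mean utility over the three visits with centre and patient random effects kept, is the primary result whatever the QQ-plots show. As protection against non-normality, report with it an interval that respects the patient and centre structure: a patient-level sandwich from that fit with the centre effect kept, or a bootstrap of patients within centre.

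Make transformed, robust and two-part fits sensitivity analyses; the planned Bayesian analysis already supplies a two-part view. Name the transformation, the robust estimator and its tuning constant in advance, and say that the robust fit uses the untransformed outcome. Keep the subgroup analyses on the untransformed specification.

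The choices can be settled without unblinding, since the sample-size re-estimation already simulated the primary analysis on blinded data from 709 patients. The cost is SAP wording, a few lines of code and possibly a slightly wider interval (0.3 to 0.7% with the sandwich in these runs).
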